***Recruitment:***

Participants will be recruited through specific advertisements placed in local newspapers, postings and promotional materials (e.g., magnets) distributed in community locations (bars, alcohol/coffee shops, grocery stores), and advertisements on free community TV channels. We have also had success with recruiting participants from postings on Craigslist and social networking sites. We have created a Facebook page for our study and have also developed our own study URL, [www.paidalcoholstudy.com](http://www.paidalcoholstudy.com), which links subjects to confidential surveys that assess some preliminary eligibility criteria and provides preliminary information about the project. We have had a lot of interest in our URL and survey, and most people who access the survey report hearing about the study through the internet (86.6%) with a minority reporting that they saw flyers in the community (7%). The results of the survey are then accessed by the research staff, and individuals who seem eligible are contacted. Individuals who call in response to ads and flyers contact us directly. Subjects will also be referred to this study by research staff on protocol #0903004912. Detailed procedures on the referral process are outlined in protocol #0903004912 and have been approved by the Yale HIC.

Each potential participant's eligibility will be assessed by a research staff member who will then contact them and set them up for the initial intake appointment. We do not anticipate any problems with recruiting these subjects since their profile is similar to that of the participants we have been recruiting for our ongoing projects and we have been quite successful in our recruitment efforts. Informed consent will be obtained from all subjects, and they will be screened by a physician for contraindicating medical or psychiatric conditions and will receive complete physical and laboratory workup, including EKG.

***Justification for Drinking Criteria:***

We will recruit alcohol-dependent or abusive heavy drinkers who consume between 20-65 drinks per week for women and 25-70 drinks per week for men. The lower limits reflect alcohol consumption that just exceeds the WHO Brief Intervention Study Group guidelines (WHO guidelines) for non-hazardous drinking, which are no more than 4 drinks/day 4-5 days per week for men (20 drinks) and no more than 3 drinks/day 5 days per week for women (15 drinks). The upper limits were chosen to ensure that we chose subjects whose typical drinking quantities would be unlikely to exceed the amount of alcohol that would be available to them for possible administration during the laboratory session. These criteria are similar to the ones being used in our ongoing work with memantine in HIC # 0602001068.

***Justification of Age Criteria and for Excluding Children and Adolescents Under 21 Years of Age:***

We will not use subjects under 21 years of age in this study. First and foremost, this is an alcohol self-administration study in which we will be offering drinkers an opportunity to consume alcohol, and in the State of Connecticut the legal age limit for drinking alcohol is 21. Secondly, subjects

below the age of 21 have probably been drinking alcohol for a shorter duration of time and will have different patterns of drinking from older drinkers, which may affect drinking during the self-administration paradigm and confound study results. The upper age limit was determined using our pilot data (see Krishnan-Sarin et al., 2007) which indicates that the majority of the subjects who participated in our ongoing study were in this age range.

***Justification for choice of memantine dose:***

We will evaluate the effects of 20 mg/day of memantine. Most clinical trials conducted with memantine in patients with dementia have used doses of 10 or 20 mg/day. Also, memantine has been used in doses of 15 and 30 mg/day in moderate, non-dependent drinkers (Bisaga and Evans, 2004) and has been shown to reduce cue-induced craving in doses of 20 and 40 mg/day in alcohol-dependent drinkers (Krupitsky et al., 2007). But most important, our choice of this dose is based on our most recent analyses of our final data, which suggests that 20 mg of memantine reduced alcohol-induced stimulation and also seemed to reduce alcohol craving and drinking. The dose of memantine will be tapered up slowly to reduce incidence of adverse events. We designed these procedures based on our experience with using memantine in the current HIC # 0602001068 project. Our data from this protocol indicates that the total number of adverse events experienced by participants receiving either the 40 mg or 20 mg dose of memantine did not differ from those receiving placebo.

***Justification for choice of naltrexone dose:***

We will use naltrexone in a dose of 50 mg/day. This is the dose of naltrexone that is FDA approved for the treatment of alcohol dependence and has been most commonly used in most clinical trials (Anton et al., 2005; O'Malley et al., 1992; Volpicelli et al., 1992) and laboratory studies (Davidson et al., 1999; O'Malley et al., 2002; Anton et al., 2004). This dose also produces complete blockade of the mu-opioid receptors (Weerts et al., 2008). The 100 mg/day dose has also shown efficacy in many recent clinical trials (e.g., Anton et al., 2006), and our own preliminary evidence suggests that this dose may produce greater reduction in drinking in FHP drinkers than the 50 mg dose. However, in the proposed "proof of concept" trial we did not want to run the risk of missing the signal for a synergistic effect of memantine or NAC by combining it with a dose of naltrexone, which had a large effect of its own. Moreover, now that we are combining two medications we want to use a lower dose of naltrexone to minimize side effects from the combined pharmacotherapy.

***Justification for choice of N-acetyl cysteine dose:***

N-acetylcysteine (NAC) is an N-acetyl pro-drug of the naturally occurring amino acid cysteine. This agent is FDA-approved for use as a mucolytic agent for bronchopulmonary disorders (e.g. Grandjean et al., 2000) and as an oral or intravenous antidote to treat acetaminophen poisoning (Smilkstein et al., 1988). We propose to use a dose of 2400 mg/day of NAC which was observed to be safe and tolerable in cocaine dependent participants (e.g. Larowe et al., 2006).

***Procedures***

**Recruitment, Baseline Assessments, Physical Exam and PIT Task**

Potential subjects will be recruited as described earlier. Participants will be scheduled for an appointment at the Substance Abuse Center in the Connecticut Mental Health Center or at the

Substance Abuse Treatment Unit, New Haven, CT, where informed consent will be obtained prior to any other procedures. Then the intake battery will be administered to assess eligibility for the study. At this intake appointment FH of alcoholism will be assessed using the FHAM (see assessments section, below). The research assistant will schedule a physical exam (including EKG) and routine laboratory work, and hepatic, kidney, and thyroid function tests will be conducted by an APRN. A detailed medical history will be obtained from all subjects and pregnancy tests for all females. Subject characteristics and medical history will be reviewed by the PI to ensure that the subject meets all the eligibility criteria. The subjects will then be scheduled to meet with the study physician ([name]), who will also review their eligibility for the study and review their medical history information and EKG. If eligible to participate, and if they have also consented to participate in the genetic study, we will draw plasma samples for this purpose. For those participants without the use of a phone or cell phone and may be difficult to reach for the next 20 appointments after the initial intake, we will provide them with a disposable study cell phone to enhance communication and attendance at all appointments. Urine will be collected to test for drugs and ethylglucuronide, a metabolite of ethyl alcohol that will be used as a biomarker of alcohol consumption at baseline and the ADP sessions.

After subjects are determined to be eligible, they will participate in the Pavlovian Instrumental Transfer (PIT) Task. This task will use a sucrose reinforcer, and so measure PIT as a general tendency and not an alcohol specific tendency. In this part of the study, subjects will be asked to taste different stimuli. The stimuli will be delivered as liquids. Stimuli will be stored in a refrigerator and brought to room temperature before use. Liquids will be delivered with our custom designed gustometer built by [name] (in collaboration with colleagues in the Pierce shop). This set up has been used successfully by [name] lab for the past 9 years (Small et al. 2003; Small et al. 2004; Veldhuizen et al. 2007; Small et al. 2008; Veldhuizen et al. 2010; Veldhuizen et al. 2011; Veldhuizen et al. 2011; Veldhuizen et al. 2012). In brief, the liquid delivery consists of a computer running E-Prime, controlling a series of programmable syringe pumps with 60ml syringes and beverage tubing attached. New tubing and syringes are used for each subject. Our stimuli will contain either a taste (juice or bitter) or a neutral solution. All solutions will be prepared in the laboratory using commercially available tastes. The tastes might include sucrose, glucose, sodium chloride, citric acid, quinine hydrochloride, sodium bicarbonate, potassium chloride, capsaicin, and artificial sweeteners such as aspartame, acesulfame potassium, and sucralose. The juice will consist of three different flavors of Gatorade that the subjects will choose.

#### Alcohol-Drinking Paradigm

The procedures for all the alcohol-drinking sessions will be similar. Participants will be asked to arrive at the Hospital Research Unit (HRU) of Yale New Haven Hospital, New Haven, at 9 am. They will be told not to consume any alcohol after 10 pm on the previous evening. We will assess breath alcohol levels upon arrival and conduct urine drug tests. If the breath alcohol levels are positive but below 0.05 and decreasing, then the participant will be allowed to continue. If the urine drug tests are positive and/or breath alcohol levels are 0.05 or greater, then the session will be rescheduled. The drinking sessions will be conducted in a private room in the HRU. The participants will stay in these rooms from time of admission to discharge.

Table1 below provides a detailed timeline of the procedures. Participants will complete the impulsivity and alcohol association tasks at the beginning of the lab session, and this data will be used to examine medication effects and relationship to drinking behaviors. The alcohol-drinking session will start at 3 pm with the priming dose period, which will be followed by three one-hour drinking periods (4-5 pm, 5-6 pm, and 6-7 pm), and will conclude at 7 pm.

- a. *Exposure to alcohol cue:* Ten minutes prior to the start of the priming dose (PD) period (i.e., 2:50 pm), the research assistant will walk into the participant's room with the glasses, the alcohol, and the mixers. The research assistant will then proceed with the mixing of the priming drink of alcohol in front of the participant. **When done, he/she will leave the drink on the table, instruct the participant not to consume the priming drink until they are told to do so and leave the room.** At 2:59 pm the research assistant will walk back into the room and ask the subject to report on how much alcohol craving they are experiencing. At 3 pm the research assistant will walk back into the room and tell the participants that they have five minutes to consume the PD of alcohol and will then again leave the room, and the PD period will commence.
- b. *Priming dose (PD) period:* The PD of alcohol that is provided at 3 pm will contain a dose of 80 proof alcohol designed to raise blood alcohol levels to 0.03 mg% of alcohol, and subjects will have 5 minutes to drink it. The purpose of the PD is to provide a standard dose for evaluating the effects of medications on the responses to a standard drink of alcohol and to model a "lapse" situation.
- c. *Absorption Period and Ratings of Ethanol Effects:* A 50-minute absorption period will follow during which the subjective and physiological effects of this priming dose of alcohol in combination with memantine will be monitored. Using this procedure, we will be able to closely monitor changes in subjective effects (alcohol craving, stimulation/sedation) during the rising and falling limbs of the blood alcohol curve.
- d. *Alcohol self-administration (SA) periods:* Following the PD, participants will be exposed to three one-hour SA periods designed to model a "relapse" situation. During each SA period they will be permitted to drink up to four alcoholic drinks designed to raise BALs by 0.015 mg% of alcohol, or to receive cash (equivalent to the price of each drink that is not consumed). The first SA period will begin at 4 pm, when the research assistant will take 4 prepared drinks into the room along with a "tab" sheet worth \$12. The participant will be informed that these 4 drinks will be available to him/her for the next 60 minutes (i.e., until 5 pm). S/he can choose either to drink or to keep the money; each drink will cost \$3. For example, if the participant chooses to drink only one drink in the next one hour, s/he will earn \$9. The money will be given to them the next morning before they leave the hospital. The second and third SA periods will begin at 5 pm and 6 pm, respectively, and will be similar to the SA period. Thus, participants can choose to consume up to 12 additional drinks over this 3-hour period or to receive up to \$36 to take home the next morning.
- e. *Beverage content and mixers:* The YNHH Investigational Pharmacy will calculate the alcohol dose for each participant. In the priming drink, the dose will be designed to raise blood alcohol levels to 0.03 mg% and will be based on the formula specified by Watson (1989) which takes into account gender, weight, and age of the subject. The subsequent drinks provided in the SD blocks are designed to raise BAL by 0.015 mg% each, using the same formula. The alcohol doses will be delivered to the HRU unit and any unused doses will be returned to the pharmacy.

Alcoholic beverages administered during this study will consist of 1 part 80 proof liquor of the subject's choosing to 3 parts mixer chosen from a selection of equicaloric, noncaffeinated, non-carbonated drinks. The research assistant will prepare the drinks

using the alcohol doses prepared by the YNHH pharmacy. Participants would have already chosen their mixers on an earlier day. Specifically, they will be asked to choose two mixers and choice of alcohol (vodka, rum etc.) from a list that will be provided to them at the intake appointment. Based on our previous experience, we have found that subjects prefer being offered a choice of alcoholic beverages and mixers, thereby providing a closer approximation to their own drinking experiences. The pharmacy will prepare 2 syringes (5cc each) of the specified liquor(s) and deliver them to the HRU the morning of or the day before the subject's ADP#1. The liquors will be mixed with the subject's chosen mixers, same ratio as drinking session (e.g. 1 part liquor to 3 parts mixer). The subject will sample each drink once settled into their room and will be instructed to swish it around in their mouth and then spit it out. Once the subject has made their selection, we'll call the pharmacy to confirm their choice. Frozen plastic cubes will be used to chill each drink without diluting them and the prepared drinks will be covered with saran wrap to avoid any evaporation of alcohol during the drinking period. Drinks will be prepared ten minutes prior to each drinking hour.

*f. Assessments during and after the three choice periods:* During the second, third and fourth hour of the laboratory session, drinking behavior will be videotaped for later analysis, and craving and stimulation/sedation will be assessed every thirty minutes. **The range of assessments, however, is limited to avoid interfering with the evaluation of drinking behavior.** In order to monitor blood alcohol levels we will draw three ml of blood from the subjects every 10 minutes during the first hour (i.e., at 2:10, 2:20, 2:30, 2:40, and 2:50). After the priming dose, blood draws (3 ml) for blood alcohol determination will occur every 60 minutes (i.e., at 4, 5, 6, 7, and 8 pm), regardless of whether the participant chooses an alcoholic beverage. This frequency of assessments provides a sensitive assessment of blood alcohol levels (as was demonstrated in our naltrexone study) without unduly disturbing the subject's drinking behavior. These changes can then be correlated to the subjective changes produced by alcohol at these same time points.

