**Table 1**

PERIOD	TIMING	PROCEDURES
ADP	10 am	Breath alcohol levels, AUQ, YCS, TLFB, SAFTEE, CADSS, Vitals Administer last doses of medications
	11 am	Approach Avoidance Task, Impulsivity tasks; Self report and Laboratory measures
	12 pm	Lunch and Smoke Break for smokers
	1 pm	Insertion of IV for blood alcohol draws
	2 pm	Start of baseline; AUQ, YCS, BAES, Vitals; Smoke break for smokers
	2:30 pm	AUQ, YCS, BAES, Vitals
	2:45pm	YCS
	2:50 pm	Alcohol cue exposure to preparation of priming drink (PD)
	2:59 pm	YCS
	3 pm	Priming dose period: Instruct participant to consume PD (0.03g/dl) in five minutes

	3:10 pm	Blood alcohol, AUQ, YCS, BAES
	3:20 pm	Blood alcohol, AUQ, YCS, Vitals
	3:30 pm	Blood alcohol, AUQ, YCS, BAES
	3:40 pm	Blood alcohol, AUQ, Vitals
	3:50 pm	Blood alcohol, AUQ, YCS, BAES
	4 pm First tray	1 st Self-administration (SA) period: Bring in first tray of 4 drinks (each designed to raise BAL by .015 g/dl) and drinking tab (\$12); Instruct participants on choice of drinks versus money.
	4:30 pm	AUQ, YCS, BAES
	5 pm Second tray	Blood alcohol, AUQ, BAES, Vitals @ 4:55 pm 2 nd SA period: Remove first tray and bring in second tray: Present participant with 4 drinks (each will raise BAL by .015 g/dl) and drinking tab (\$12); repeat instructions
	5:30 pm	AUQ, YCS, BAES
	6 pm Third tray	Blood alcohol, AUQ, BAES, Vitals @ 5:55 pm 2 nd SA period: Remove second tray and bring in third tray: Present participant with 4 drinks (each will raise BAL by .015 g/dl) and drinking tab (\$12); repeat instructions
	6:30 pm	AUQ, YCS, BAES
	7 pm	Blood alcohol, AUQ, BAES, YCS, Vitals
	7:30 pm	Dinner
	8 pm	Breath Alcohol, AUQ, YCS, BAES, Vitals
	9 pm	Breath Alcohol, AUQ, YCS, BAES, Vitals
	10 pm	Breath alcohol, AUQ, YCS, BAES, Vitals
Discharge	7 am	Breath alcohol, AUQ, YCS, Vitals, CADSS, BPRS

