g. *End of alcohol self-administration period and overnight stay in HRU:* The alcohol administration portion of the study will end at 7:05 pm. Following this, breath alcohol levels and craving will be assessed every 30 minutes until the subject's breath alcohol level falls below 0.02. Participants will then be given dinner and will stay in the hospital overnight. This overnight stay will serve multiple purposes: 1) to ensure that subjects do not continue to drink following exposure to alcohol in this paradigm, 2) to ensure that they are safe and are not discharged while still intoxicated, and 3) to motivate subjects to drink during the session by ensuring that they do not have an opportunity to have access to more alcohol later that same day. The next morning participants will be assessed using craving and withdrawal measurements, they will be provided with breakfast, and they will then be discharged between 8 and 9 am.

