- d) *The Implicit Association Test (IAT)* (Greenwald et al., 2003): This task measures implicit affective associations with the alcohol. Using a computerized sorting task, individuals simultaneously classify two target conditions, 'alcohol' (ie., wine, beer, pint, vodka, whiskey, wine cooler) versus 'soft drink' (coca cola, juice, orange soda, root beer, sparkling water, 7-up), and two affective categories relevant to drinking, 'pleasant' (ie. talkative, excited, cheerful, happy, funny, lively), versus 'unpleasant' (i.e., nauseous, listless, awful, miserable, sad, annoying). IAT effects will be calculated with the D600 scoring algorithm. Internal consistency for bipolar alcohol-related affective IAT was .79 in (Houben, in press); the bipolar IAT predicted drinking above explicit measures and outperformed five other variants of the IAT(e.g., unipolar positive, unipolar negative IAT).
- e) *A Pavlovian Instrumental Transfer Test (PIT)* will be completed to examine individual variation in the ability of incentive stimuli to control behavior. This task will use a sucrose reinforcer, and so measure PIT as a general tendency and not an alcohol specific tendency. Prior studies have explored the neural mechanisms of PIT with monetary (Talmi et al., 2008) and juice reinforcement (Bray et al., 2008). PIT involves three distinct training phases: (1) a Pavlovian phase, (2) an instrumental learning phase and (3) a transfer phase. Multiple trials occur in each phase.
- g) Ratings of Drinking Behavior During the Alcohol Self-Administration Period: Subjects will be videotaped during the alcohol self-administration portion of the study on Day 6. These videotapes will be rated by two independent raters who will indicate the onset and offset of each sip of alcohol. Using this data, dependent measures will be constructed including time until the first sip and average time to consume each drink.
- h) Blood Alcohol Levels: Blood samples will be drawn to measure plasma levels of blood alcohol (BAC) during the priming dose and during the alcohol self-administration paradigm on day 6. Blood samples will be stored at -4°C and will be analyzed using gas chromatographic techniques at the HRU Laboratory.

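### The drinking-session text times five blood alcohol draws before the 3 pm priming drink, and the stated 100 ml blood total covers one session, not three

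*Combined protocol and SAP*

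**What the plan says.** **Session clock.** Section V.3, Alcohol-Drinking Paradigm, states: "The alcohol-drinking session will start at 3 pm with the priming dose period". Paragraphs a and b and Table 1 also put the priming drink at 3 pm. The three choice periods run 4–5, 5–6 and 6–7 pm.

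**Purpose of early sampling.** Paragraph c describes a 50-minute absorption period in which staff will "closely monitor changes in subjective effects (alcohol craving, stimulation/sedation) during the rising and falling limbs of the blood alcohol curve". Item h (Blood Alcohol Levels) under Assessments says samples will "measure plasma levels of blood alcohol (BAC) during the priming dose" and during self-administration.

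**Draw times in the text.** Paragraph f says staff will "draw three ml of blood from the subjects every 10 minutes during the first hour (i.e., at 2:10, 2:20, 2:30, 2:40, and 2:50". For the hours that follow the priming drink it adds: "blood draws (3 ml) for blood alcohol determination will occur every 60 minutes (i.e., at 4, 5, 6, 7, and 8 pm".

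**Draw times in Table 1.** Blood alcohol is listed at 3:10, 3:20, 3:30, 3:40 and 3:50 pm (the 3:10 entry reads "Blood alcohol, AUQ, YCS, BAES"), then at 4:55, 5:55 and 7 pm. None is listed between 2 and 3 pm, and none at 4 pm. The 8 pm entry is "Breath Alcohol, AUQ, YCS, BAES, Vitals". Paragraph g agrees with breath testing at that stage: once drinking ends, "breath alcohol levels and craving will be assessed every 30 minutes" until the level is below 0.02.

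**Blood volume.** Section IX.1, item 9, counts about 40 cc at intake, 30 cc for genetics and about 30 cc for self-administration, which it places in the fourth phase. It totals these as 100 ml (about 3.4 oz) and compares that with a guideline of 450 cc in eight research weeks. Section V.3 gives every participant three drinking sessions with similar procedures, in Phases 2, 3 and 5. Phase 4 is the washout.

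**The concern.** The protocol gives two clock times for the same five draws, and the version in the text cannot serve its stated purpose: before the drink there is no rise or fall to follow. An IV is in place from 1 pm, so draws at 2:10 to 2:50 are physically possible and the text could be carried out as written. The absorption period would then have no blood alcohol value. The pairing that paragraph f mentions, of blood alcohol with subjective ratings at the same time points, could not be made for that hour.

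The blood total matters for a different reason. It is the figure in the risk section that supports the statement that the volume guideline is met, and it leaves out two of the three sessions.

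**Working it through.** **1. Which clock is right?** Measure each time in paragraph f from the 3 pm drink.

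- As written (2:10, 2:20, 2:30, 2:40, 2:50): −50, −40, −30, −20, −10 minutes.
- One hour later: +10, +20, +30, +40, +50 minutes, which are Table 1's times exactly.

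Paragraph f places these draws in the first hour and treats the second to fourth hours as the choice periods. Those run 4–7 pm, so its own first hour is 3–4 pm. Paragraph c, Assessments item h and Table 1 agree.

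**2. What would the literal reading lose?** Table 1 ratings from 3:10 to 3:50 pm that have a blood value at the same time:

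| Rating | Times in Table 1 | Literal paragraph f | Table 1 |
|---|---|---|---|
| BAES | 3:10, 3:30, 3:50 | 0 of 3 | 3 of 3 |
| YCS | 3:10, 3:20, 3:30, 3:50 | 0 of 4 | 4 of 4 |
| AUQ | all five | 0 of 5 | 5 of 5 |

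**3. Does any specified analysis use blood alcohol?** Section V.4 names drinks consumed and drinking-pattern measures (Aim 1), YCS and AUQ craving (Aim 2), BAES stimulation and sedation (Aim 3), and exploratory work on adverse events, task and impulsivity measures, and genotypes. None has blood alcohol as an outcome or covariate.

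**4. Reproduce the 100 ml.** Inputs: 40 cc intake and 30 cc genetics (Section IX.1); 5 + 5 = 10 draws of 3 ml (paragraph f).

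- One session: 10 × 3 = 30 ml.
- Total with one session: 40 + 30 + 30 = 100 ml, the stated figure.

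Table 1's eight draws would give 8 × 3 = 24 ml and 40 + 30 + 24 = 94 ml. The stated figure therefore matches paragraph f's ten draws in a single session.

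**5. Three sessions.** Table 1 gives no volumes, so 3 ml per draw is carried over from paragraph f.

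| | Ten draws (paragraph f) | Eight draws (Table 1) |
|---|---|---|
| Session blood | 3 × 30 = 90 ml | 3 × 24 = 72 ml |
| Total with genetics | 40 + 30 + 90 = 160 ml | 40 + 30 + 72 = 142 ml |
| Excess over 100 ml | 60% | 42% |
| Share of 450 cc | 160/450 = 36% | 142/450 = 32% |
| Total without genetics | 40 + 90 = 130 ml | 40 + 72 = 112 ml |

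The genetics sample is optional (Section IX.1, item 12). Every version exceeds 100 ml.

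**The case against.** The best reply is that the document already corrects itself. The section introduces Table 1 as the detailed timeline, Table 1 has the right times, and staff would have to follow one sentence against the session's own 3 pm start. This largely stands. The zeros in step 2 describe a literal reading that the rest of the protocol contradicts, and they are not an expected loss of data. Paragraph f also says only that blood alcohol can be correlated with ratings; it does not commit to an analysis.

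A reader might take the 2:10–2:50 draws as deliberate pre-drink baselines. The 2 pm baseline row and the 1 pm IV make that possible, but it conflicts with the first-hour wording, the stated purpose of the sampling, and a table that lists no blood at those times.

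A reader might also infer that the aims are compromised or the safety limit breached. Neither follows. The hypotheses of Aims 1 to 3 concern the self-administration period, no specified analysis uses blood alcohol, and 160 ml is far below 450 cc.

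Finally, it is tempting to let Table 1 settle everything: delete the 4 pm draw and put 142 ml in the risk section. The documents do not support that. Paragraph f expressly schedules 4 pm, and the stated 30 cc matches its ten draws, not Table 1's eight. If ten are taken, 142 ml would understate the volume again. Breath at 8 pm is better supported, by Table 1 and paragraph g, but it still needs the sponsor's confirmation.

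**Conclusion.** Both errors hold, and both are minor. The five times in paragraph f are one hour early. The blood total is too low by as much as 60 ml (42 ml on Table 1's draws, and less without genetics). The first is an internal inconsistency and the second a misstated safety figure; neither is a design choice. The hypotheses, the specified analyses and the conclusion on the 450 cc guideline are unchanged.

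The volumes assume 3 ml per draw in all three sessions. They exclude any repeat laboratory blood work, which Section X.2 foresees without giving a volume. The protocol's phase label is also wrong, though trivially so: the printed phase list itself skips a number.

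**What to change.** - **Section V.3, paragraph f:** change the five times to 3:10, 3:20, 3:30, 3:40 and 3:50 pm, and state that Table 1 governs these draws. Leave paragraph g's half-hourly breath testing in force.
- **Sponsor to confirm:** whether blood is drawn at 4 pm, and whether the 8 pm sample is blood or breath. Then make paragraph f and Table 1 agree.
- **Section IX.1, item 9:** replace the fourth phase with Phases 2, 3 and 5. Restate session blood as up to 90 ml and the total as up to about 160 ml including the optional genetics sample. If only Table 1's eight draws are taken, the total is 142 ml; without genetics the totals are 130 ml (ten draws) or 112 ml (eight). The statement that the guideline is met can stay.

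The cost is a few wording changes and one query to the sponsor. No visit, sample, staff time or analysis is added.
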